## STUDY PROCEDURES

### *1. Procedures*

#### *Subjects*

Subjects will be 310 smokers who have been diagnosed with HIV/AIDS, meet study eligibility criteria, and provide written consent to participate in this between-subject trial.

## *Study Procedures*

### **Initial Eligibility Screening.**

Recruited subjects will complete an initial eligibility assessment in the HIV/AIDS clinic or over the telephone. This assessment reduces the likelihood that participants attend an Intake Session only to learn that they are ineligible or to allow us to ascertain physician's clearance should the participants have a medical condition that requires approval. Subjects who pass this pre-screening will be invited to attend an Intake Session.

### **Intake Session (Week -1): Consent, Eligibility Determination, Baseline Measures.**

Subjects who pass the pre-screening will be invited to attend a 2.5-hour Intake Session where the following activities will occur:

1. Subjects will hear a study description where all study procedures, risks, and information about the study medication will be reviewed. Subject questions will be answered. Following this presentation, the combined informed consent and HIPAA form will be completed.
2. A urine pregnancy test (all female subjects) will be administered.
3. A breath alcohol concentration assessment (BrAC) to control for alcohol consumption. The handheld device uses a disposable mouthpiece, reports the concentration of alcohol in breath and takes about 2 minutes.
4. A carbon monoxide (CO) breath assessment to control for prior tobacco exposure. The handheld device uses a disposable mouthpiece, reports CO in parts per million (ppm), and takes about 3 minutes.
5. Mental status examinations (Mini International Neuropsychiatric Interview, HADS, C-SSRS, and MADRS, YMRS, Bipolar Disorder Additional Screener, if necessary) with a trained research staff member.
6. Complete routine medical history, including blood pressure assessment.
7. A concomitant medication review.
8. Complete baseline paper and pencil measures to assess 1) background variables that may serve as covariates and will allow for the assessment of the study's external validity (e.g., smoking history, demographics), 2) mediators (e.g., affect, cognition), 3) moderators (e.g., disease-related information, and 4) baseline smoking behavior.
9. Provide one 10ml blood sample (2 teaspoons) to assess nicotine metabolite ratio (cotinine and 3-hydroxycotinine).
10. Provide one 10ml blood sample (2 teaspoons) for DNA collection and genotyping.

Initially eligible participants who have not had kidney function tests within the last 6 months (as ascertained by medical record review or provision of results from the participant's health care provider) will provide one 10ml blood sample (2 teaspoons) to complete these tests following the Intake Session. Test results that are outside of normal ranges will be reviewed for final eligibility by the Study Physician prior to enrollment.

If eligible at this point, subjects will be scheduled for the first treatment session (Week 0).

### **Behavioral Counseling (Week 0-Week 9).**

All subjects will receive manual-based counseling from a counselor trained and supervised by [name]. The counseling protocol is based on PHS guidelines for smoking cessation treatment (Fiore et al., 2008), used in our studies with cancer patients ([name] et al., 2010a) and the general population of smokers ([name] et al., 2010b; R01 DA025078). Counseling is included given its efficacy at helping smokers quit (Fiore et al., 2008).

to ensure that participants in the placebo arm receive active treatment to quit smoking and to increase study retention. Counseling is provided to both treatment arms until Week 9 to equate for time and attention across arms since this method was used in past varenicline trials (e.g., Gonzales et al., 2006). Counseling will be provided in-person at the CIRNA. Sessions can be arranged at convenient times for the participants, including evenings.

**Pre-Quit Session (Week 0):** The counseling program begins at Week 0 with a 1-hour in-person “pre-quit” counseling session to prepare for the target quit day. This session focuses on reviewing the participant’s history and experience with quitting as well as beliefs about smoking, quitting and perceived barriers to cessation. A quitting plan is initiated and involves identifying smoking triggers and strategies to increase the chance for success, including relying on social support to quit smoking and altering behaviors associated with smoking. The first 3 weeks of medication is dispensed at this session and will begin at the session or immediately following the session.

**Quit Day Session (Week 1):** At Week 1, participants will receive a 30-minute in-person “quit-day” session to review the initial quit attempt, identify potential reasons for relapse, and review a plan for avoiding tempting situations.

**Relapse Prevention Sessions (Weeks 3, 5, 7, and 9):** Participants will then receive 4 additional 20-minute in-person booster sessions at Weeks 3, 5, 7, and 9 which focus on either reinforcing success and reviewing the quit plan or reestablishing a quit date and restarting the cessation process. The counseling sessions are designed to enhance awareness of the harmful effects of smoking, assist the person in developing skills to quit and avoid relapse, and instruct the smoker on varenicline use. Lastly, all counseling sessions may be audiotaped and a random 15% of sessions assessed for protocol adherence. The counselor is blind to randomization.

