#### Supply, Preparation, Storage, Packaging and Dispensing of Study Medication

Varenicline and matching placebo, provided at no-cost by Pfizer, will be packaged and stored at the University of Pennsylvania Investigational Drug Service. Varenicline and matching placebo will be packaged into blister packs in 1-2 week supplies. Medication will be distributed to participants in increments at Weeks 0, 3, and 7.

IDS will oversee the randomization and labeling of all study medication, and will assign each kit, which contains 12 weeks of medication for one subject, and a unique Pharmacy Randomization Number (PRN). Once a new subject is enrolled and eligible, IDS will assign the subject the next available PRN. The research staff will then label the blister packs with the subject's study ID number. The PRN and study ID number must match for each blister pack a subject receives. Medication kits will be stored in a locked cabinet at our center until they are dispensed at participant medication pick-up visits.

Regular study drug reconciliation will be performed to document drug assigned, drug consumed, and drug remaining. This reconciliation will be logged on the drug reconciliation form, and signed by the research staff member who completed the reconciliation.

At the completion of the study, there will be a final reconciliation of drug shipped, drug consumed, and drug remaining. This reconciliation will be logged on the drug reconciliation form, signed and dated by the research staff. Any discrepancies noted will be investigated, resolved, and documented prior to return or destruction of unused study drug. Drug destroyed on site will be documented in the study files.

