**Varenicline or Placebo Treatment (Weeks 0-12).**

The dosing regimen used in past varenicline trials and consistent with FDA guidelines will be used: Day 1-Day 3 (0.5mg once daily); Day 4-Day 7 (0.5mg twice daily); and Day 8-Day 84 (1.0mg twice daily). Medication and matching placebo will be packaged into blister packs in 1-2 week supplies. Medication will be distributed in increments at Weeks 0, 3, and 7. Day 1 of study medication will be scheduled no more than 60 days following the Intake Session. If Day 1 is scheduled more than 60 days following the Intake Session, the participant will be required to attend another Intake Session in order to reaffirm eligibility. Participants who discontinue the study medication for 14 or more consecutive days will require approval from the Principal Investigator and Study Physician before restarting the study medication.

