**Varenicline Adherence.**

At each session after Pre-Quit until end of treatment, participants are evaluated in terms of their adherence by self-report and pill count. At Weeks 3 (steady-state) and 12 (end of treatment), participants will be asked to provide blood samples to evaluate varenicline levels as a measure of adherence. Specific strategies to address non-adherence will be used if necessary. The varenicline adherence approach formally assesses participant reasons for non-adherence using scenarios and uses specific strategies to enhance compliance. If the participant discontinues study medication for any reason for 14 or more consecutive days prior to an adherence blood draw, the blood draw will not be conducted.

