**Table 2: Study Measures/Events**

Study Week	-1	0	1	3	5	7	9	12	18	24
Session Name	Intake	Pre-Quit	TQD	W3	W5	W7	W9	W12	W18	W24
TREATMENT										
Varenicline/Placebo		X	X	X	X	X	X	X	X	
Counseling		X	X	X	X	X	X			
SCREENING/COVARIATES										
Urine Pregnancy Screen	X									
Breath Alcohol Concentration	X									
Blood Pressure	X	X	X	X	X	X	X	X	X	X
Depression/Anxiety (HADS)	X	X	X	X	X	X	X	X	X	X
Demographics	X									
Smoking History/FTND	X									
ETOH History	X									
Medical History	X									
Psychiatric History (MINI)	X		X g							
Adherence to Antiretrovirals Instrument		X			X		X	X	X	X
Pharmacy Refill Data		X d			X d			X c		X c
Concomitant Medications	X	X	X	X	X	X	X	X	X	X
Creatinine Clearance	X a									
Viral Load Assessment								X e		
Nicotine Metabolite Ratio	X									
Genetic Polymorphisms	X									
Bipolar Disorder Symptoms (MADRS f , YMRS, Additional Screener, MINI) g	X		X	X	X	X	X	X	X	X
MEDIATING VARIABLES										
Affect (PANAS)		X	X	X		X		X		
Cognitive Function (N-back, CPT)		X	X	X				X		
Nicotine Withdrawal (MNWS-W)		X	X	X		X		X		
Smoking Urges (QSU-B)		X	X	X		X		X		
TREATMENT VARIABLES										
Adherence (Pill Count)			X	X	X	X	X	X		
Adherence (Blood)				X i				X i		
Side Effects Checklist (SEC)		X	X	X	X	X	X	X	X	X
Side Effects (Open-Ended)			X	X	X	X	X	X	X	X
Suicidality (C-SSRS)	X	X	X	X	X	X	X	X	X	X
OUTCOMES										
Carbon Monoxide (CO) Test	X	X	X	X	X	X	X	X	X	X
Smoking Rate (TLFB)		X	X	X	X	X	X	X	X	X
Urine Cotinine								X b	X b	X b
Quality of Life (HAT-QoL)		X	X	X	X	X	X	X	X	X
ACASI-SHQ h				X		X		X		
HVTN Social Impact Assessment h				X		X		X		
Client Evaluation Form h								X		

\*TQD = Target Quit Day

\*W= Week

\*Note: Target Quit Day visit may occur +3 days from target date; Week 3, 5, 7, 9, 12, 18, and 24 visits may occur +/- 1 week from target date.

a Will only be completed on initially eligible participants who have not had this test within last 6 months.

b Will only be completed on participants who self-report abstinence for  $\geq$  7 days prior to the assessment.

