### Blood Pressure

Participants presenting at intake with a blood pressure reading above 160 mmHg systolic and/or 100 mmHg diastolic will be ineligible for the study. Participants presenting with an elevated blood pressure reading between 150-160 mmHg systolic and/or 90-100 mmHg diastolic at intake will have a second blood pressure reading taken after a ten minute period in which the participants will be instructed to sit comfortably. If, after the second reading:

- A participant has a blood pressure between 150-160 mmHg systolic and/or between 90-100 mmHg diastolic, the medical staff will evaluate the situation and the participant may be deemed ineligible for the study.
- A participant has a blood pressure reading above 160 mmHg systolic and/or 100 mmHg diastolic, s/he will be ineligible for the study.

Blood pressure will be measured at each study visit. If participants present with elevated blood pressure (above 160 mmHg systolic and/or 100 mmHg diastolic) at any visit following the Intake Session, the study physician will be notified to determine how to proceed. If the elevated blood pressure reading occurs during a medication distribution visit (Pre-Quit, Week 3 or Week 7), no medication may be distributed until the study physician is contacted to evaluate the situation. A record of this evaluation will be recorded and sent to the study physician by email and will be stored in the participant's chart.

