mediators from baseline to week 3, since abstinence-induced withdrawal effects typically peak within the first 3 weeks of cessation (Hughes, 2007) but we can examine delayed changes to weeks 5, 7, and 9 as well. We will then assemble the path model using “seemingly unrelated estimation” methods (Beasley, 2008; Zellner, 1962). The path model partitions the effect of treatment on outcome into direct (and unexplained) effects vs. mediated effects. We will then test the overall mediation hypothesis using the proportion of treatment effect explained (Lin et al., 1997; Vittinghoff & McCulloch, 2009), and the strength of each mediating pathway as follows. We will estimate the model for standardized treatment predicting abstinence without mediators to estimate the direct effect of treatment in the unadjusted model ( $\beta^*$ ). We will then test whether treatment predicts each of the suspected mediators and, in turn, test whether mediators predict abstinence in an adjusted treatment model and estimate the effect of treatment in the mediator adjusted model  $\hat{\beta}^*$ . Finally, we will calculate the proportion of treatment effect explained, which is calculated as  $(\hat{\beta}^*/\beta^*)$ ; the standard error for this quantity is calculated using the delta method, and the mediation hypothesis will be tested using a z-test. Individual pathways will be tested using products of the coefficients along each path using a delta-method based z-test.

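### A Week 3 visit inside its window can fall up to 7 days after the Week 0 supply has run out, so late attenders may have the Week 3 mediators and drug level measured off drug

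*Combined protocol and SAP*

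**What the plan says.** **Supply.** Under Behavioral Counseling, the Pre-Quit Session text for Week 0 reads: "The first 3 weeks of medication is dispensed at this session and will begin at the session or immediately following the session". The section on Varenicline or Placebo Treatment gives the dispensing times: "Medication will be distributed in increments at Weeks 0, 3, and 7". The Blood Pressure section independently lists the same three occasions: "during a medication distribution visit (Pre-Quit, Week 3 or Week 7". The Supply and Dispensing section describes each kit as one "which contains 12 weeks of medication for one subject" and mentions no overage.

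**Dosing.** The regimen runs without a break from Day 1, and its last step is "Day 8-Day 84 (1.0mg twice daily".

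**Visit window.** The note to Table 2 states: "Week 3, 5, 7, 9, 12, 18, and 24 visits may occur +/- 1 week from target date".

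**What is measured at Week 3.** The first Varenicline Adherence section says: "At Weeks 3 (steady-state) and 12 (end of treatment), participants will be asked to provide blood samples". Table 2 puts the PANAS and the cognitive tasks at the same visit. The Aim 3 analysis focuses on changes in "mediators from baseline to week 3, since abstinence-induced withdrawal effects typically peak within the first 3 weeks of cessation".

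**Rules on time off drug.** After 14 or more consecutive days off medication, restarting needs approval. The blood draw is skipped at the same threshold. No rule covers a shorter interruption.

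**The concern.** Each passage is reasonable alone, but together they leave no margin. The Week 0 issue ends when the Week 3 visit is due, and the window lets that visit happen a week later. The interruption needs no missed dose and no protocol deviation; it follows from obeying the dispensing and window rules exactly.

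What is at stake is mainly Aim 3. Its principal mediator change is measured at the visit that the gap precedes. Placebo participants who run out lose no active drug, while varenicline participants do, so the contrast between arms in affect and cognition would tend to be diluted among late attenders. The Week 3 blood level is also affected. It is meant to represent steady state and to help validate self-report and pill count, but in these participants it would partly reflect the dispensing schedule rather than their behaviour.

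**Working it through.** No figure is given in the plan for this point, so the check is a count of days.

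**Inputs.** Week 0 is day 0.
- Week 0 issue: 3 × 7 = 21 days of drug (Pre-Quit Session).
- Start offset *s*: 0 if dosing begins on the Week 0 day, 1 if it begins the next day.
- Week 3 target: day 21, with a shift *w* from −7 to +7 days (Table 2 note), so the visit falls between day 14 and day 28.
- Kit: 12 weeks, or 84 days. The intervals Weeks 0–3, 3–7 and 7–12 need 3 + 4 + 5 = 12 weeks, so the kit matches Day 84 exactly, with nothing over.

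**Gap before the Week 3 visit**, with full adherence:

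gap = max(0, (21 + w) − (s + 21)) = max(0, w − s)

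| Visit shift *w* | Dosing starts at Week 0 (s = 0) | Dosing starts next day (s = 1) |
|---|---|---|
| −7 or 0 | 0 days | 0 days |
| +1 | 1 | 0 |
| +3 | 3 | 2 |
| +6 | 6 | 5 |
| +7 | 7 | 6 |

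The largest gap is 7 days, and 7 < 14, so neither the restart rule nor the blood-draw rule applies. The sample would still be taken.

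**Week 7.** The documents do not state the quantity issued at Week 3. Assume exactly 4 weeks (28 days) and target dates fixed from Week 0, with s = 0.
- Week 3 on target, Week 7 at +7: the second issue covers days 21–48, the visit is on day 56, and days 49–55 are uncovered. Total 7.
- Week 3 at +7, Week 7 at +7: days 21–27 are uncovered, then the second issue covers days 28–55, up to the visit on day 56. Total 7.
- Week 3 at +3, Week 7 at +7: days 21–23 are uncovered, the second issue covers days 24–51, and days 52–55 are uncovered. Total 3 + 4 = 7.

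In general the total by Week 7 is max(0, w₃, w₇), which cannot exceed 7 days.

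**End of treatment.** With Week 7 at +7 and the remaining 35 days issued, drug covers days 56–90, so the last dosing day is Day 91. The Week 12 target is day 84, with a window to day 91. The documents do not say whether postponed tablets are taken after Day 84. If they are not, up to 7/84 = 8.3% of dosing days are lost. If they are, total exposure is unchanged.

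**Sensitivity to the anchor.** The documents do not say what the target dates are counted from. If Week 3 were counted from a quit-day visit held at its limit of +3 days, the maximum would be (21 + 3 + 7) − 21 = 10 days. That reading is an assumption.

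**The case against.** The best defence is that this is a missing margin rather than a conflict of statements, and that it may never be reached. Seven days is the extreme: any missed dose leaves tablets over and shortens the gap. The Supply section refers to pick-up visits and 1–2 week packs, and Training and Quality Assurance defers visit procedures to a Manual of Operations that is not among the documents. That manual could provide extra supply. However, nothing in the text reviewed does so, and the Blood Pressure section names only three distribution visits. The defence limits the size of the problem but does not remove it.

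Several stronger readings are tempting and are not supported:

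- A reader might add a week at Week 3 to a week at Week 7 and reach 14/84 = 17%. With fixed target dates this is wrong, as shown above. It would need targets that reset from actual visits, which the documents do not describe.
- A reader might infer that the gap would go unnoticed. Pill count, self-report by timeline follow-back and collection of used blister packs at treatment visits would record it. What is missing is any rule linking a gap shorter than 14 days to the Week 3 analyses.
- A reader might infer that the gap falls when withdrawal is worst. The Aim 3 text says only that withdrawal effects typically peak somewhere within the first three weeks of cessation.
- A reader might infer that the drug effect is absent at a late Week 3 visit, or that the Aim 1 difference in quit rates is reduced. The documents give no half-life or washout period, a visit one day late is not comparable with one seven days late, and postponed doses may leave total exposure unchanged. Neither inference can be shown.

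The plan's adherence covariate and its adjustment for compliance are also a partial answer. But a proportion of total dose taken does not show whether someone was off drug on the day of the Week 3 measures.

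**Conclusion.** The point stands in a limited form. Followed exactly, the dispensing and window rules can interrupt dosing that the plan specifies as continuous, for up to 7 days before the Week 3 visit (6 if dosing starts the day after Week 0). Week 7 has the same zero margin if the Week 3 issue is exactly four weeks, with at most 7 days in total by then.

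This rests on full adherence, no spare packs, target dates fixed from Week 0 and a visit at the late edge of the window. For Aim 3 the expected direction is dilution of the treatment-to-mediator path at its main time-point. Its size, and the proportion of participants affected, cannot be computed, because the documents give neither the rate of late visits nor the drug's time course after the last dose. It merits correction because it touches a named aim and costs little to put right.

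**What to change.** 1. Reconcile the dispensing text (Supply and Dispensing, Pre-Quit Session, Varenicline or Placebo Treatment) with the window note to Table 2, so that a Week 3 or Week 7 visit inside its window cannot fall after the issued supply has run out. Which passage changes is for the investigators to decide. State also what the target dates are counted from.
2. Derive days since last dose at the Week 3 visit, in both arms, from the timeline follow-back already planned.
3. Add a sensitivity analysis of the Week 3 mediators and drug level that excludes participants assessed after their supply ended. For the mediators, apply the same rule in both arms. Because the exclusion depends on when people attended, it should stand beside the analysis of all participants and not replace it.

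The cost is protocol wording, one derived variable and one extra analysis. The full kit is already held at the centre in 1–2 week packs, so no new supply is needed. Depending on which passage is changed, the downside is a tighter visit window or slightly more drug in hand between visits.

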**Varenicline or Placebo Treatment (Weeks 0-12).**

The dosing regimen used in past varenicline trials and consistent with FDA guidelines will be used: Day 1-Day 3 (0.5mg once daily); Day 4-Day 7 (0.5mg twice daily); and Day 8-Day 84 (1.0mg twice daily). Medication and matching placebo will be packaged into blister packs in 1-2 week supplies. Medication will be distributed in increments at Weeks 0, 3, and 7. Day 1 of study medication will be scheduled no more than 60 days following the Intake Session. If Day 1 is scheduled more than 60 days following the Intake Session, the participant will be required to attend another Intake Session in order to reaffirm eligibility. Participants who discontinue the study medication for 14 or more consecutive days will require approval from the Principal Investigator and Study Physician before restarting the study medication.

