### 3. Key Inclusion Criteria

Eligible subjects will be males and females:

1. 18 years of age or older who self-report smoking at least 1 cigarette (menthol and non-menthol) per day, on average.
2. Diagnosed with HIV infection and exhibiting viral load of  $\leq 1000$  copies/mL within the last 6 months.
3. Exhibiting CD4+ count of  $\geq 200$  cells/mm^3 within the last 6 months.
  1. If the participant has not had a CD4+ count test completed in the last 6 months, an older result ( $\geq 200$  cells/mm^3) may be used if evidence is provided that all subsequent viral loads results are  $\leq 1000$  copies/mL.
4. Able to use varenicline safely, based on a medical evaluation including medical history and psychiatric evaluation.
5. Residing in the geographic area for at least 7 months.
6. Women of childbearing potential (based on medical history) must consent to use a medically accepted method of birth control (e.g., condoms and spermicide, oral contraceptive, Depo-Provera injection, contraceptive patch, tubal ligation) or abstain from sexual intercourse during the time they are taking study medication and for at least one month after the medication period ends.
7. If current or past diagnosis of bipolar disorder (I, II, or NOS), eligible if:
  - a. No psychotic features
  - b. MADRS: total score  $\leq 8$  (past 4 weeks), suicidal item score  $\leq 1$  (past 4 weeks)
  - c. Y-MRS: total score  $\leq 8$  (past 4 weeks), irritability, speech content, disruptive, or aggressive behavior items score  $\leq 3$  (past 4 weeks)
  - d. No psychiatric hospitalization or Emergency Room visits for psychiatric issues in the past 6 months

- e. No aggressive or violent acts or behavior in the past 6 months
- 8. Able to communicate fluently in English.
- 9. Capable of giving written informed consent, which includes compliance with the requirements and restrictions listed in the combined consent/HIPAA form.

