## **Screening/Covariate Measures.**

### Urine Pregnancy Screen

The urine pregnancy screen will assess for current pregnancy in all women and will be administered at the Intake Session.

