#### **5. Tissue Specimens**

##### Blood.

Because, on average, the quality of DNA that is extracted from blood is superior to the quality of DNA that is extracted from saliva, we are asking participants to provide 2 tubes of blood (up to 20mL or 1.5 tablespoons) at the Intake Session for genetic analysis (NMR & other genetic polymorphisms). Given that the complete predictive validity of the genotypes under study are not fully known at this time, participants will not be informed of the test results. All specimens are to be collected solely for research purposes.

One 10mL sample of blood will be drawn at two sessions (Weeks 3 and 12) to evaluate varenicline adherence, unless the participant has not taken the study medication for 14+ days.

An 8.5mL blood sample may also be collected following Intake to assess creatinine clearance in participants who have not had these assessments within the past 6 months.

Urine. A urine sample will be required from females at the Intake Session for pregnancy screening. Subjects who have a positive pregnancy test will be deemed ineligible. Urine samples will also be collected at Weeks 12, 18, and 24 to assess urine cotinine levels.

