Participants will also be told that varenicline may impair their ability to perform tasks requiring judgment or motor and cognitive skills and that they should proceed with caution in this regard until they are certain that varenicline does not affect their performance. Participants will be told that varenicline may be associated with somnambulism (sleep walking) that may result in harmful behavior to self, others, or property, and if they notice such behaviors that they should discontinue varenicline and notify the study staff after seeing their medical provider. Participants will also be advised that Chantix may affect their response to alcohol including lower alcohol tolerance, aggressive behavior, or impaired memory following consumption of alcohol. Participants will be instructed to minimize alcohol intake (no more than 3 drinks per occasion or within a 24-hour time period) while taking varenicline. Participants will be advised to inform the study staff if they are taking or plan to take any prescription or over-the-counter drugs. Women will be advised to notify the study staff if they become or intend to become pregnant during the study period. The research team has extensive prior experience conducting smoking cessation trials with varenicline.

**Reproductive Risks.** Because varenicline safety for an unborn baby is unknown, participants will be told that they should not become pregnant while on this study. Women taking study medication should not nurse a baby. If the woman is of childbearing potential, she must use an adequate form of contraception while study medication is being taken and for at least one month after the medication period. If the woman is pregnant or breast feeding, she may not participate in this study, and if she becomes pregnant during the study, study medication will be immediately discontinued and the woman will be permitted to continue with counseling and assessments only. Women will be asked to take a pregnancy test before starting the study.

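### Pregnancy is tested only at Intake, up to 60 days before the first dose, and required contraception does not start until dosing does

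*Combined protocol and SAP*

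**What the plan says.** **Testing.** The Intake Session list (item 2) says "A urine pregnancy test (all female subjects) will be administered". The Urine Pregnancy Screen section says "The urine pregnancy screen will assess for current pregnancy in all women and will be administered at the Intake Session", and the Tissue Specimens section says "A urine sample will be required from females at the Intake Session for pregnancy screening". Table 2 has a single mark for this screen, under Week -1.

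**First dose.** Under Pre-Quit Session (Week 0) the protocol says "The first 3 weeks of medication is dispensed at this session and will begin at the session or immediately following the session".

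**Interval.** The section on varenicline or placebo treatment says "Day 1 of study medication will be scheduled no more than 60 days following the Intake Session". A later start requires a new Intake Session to reconfirm eligibility. The note to Table 2 gives visit windows for Target Quit Day ("Target Quit Day visit may occur +3 days from target date") and for Weeks 3 to 24, but none for Pre-Quit.

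**Contraception.** Key Inclusion Criteria, item 6, requires women of childbearing potential to agree to use birth control "or abstain from sexual intercourse during the time they are taking study medication and for at least one month after the medication period ends". The Reproductive Risks paragraph gives the same period: "she must use an adequate form of contraception while study medication is being taken and for at least one month after the medication period".

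**Other safeguards.** Medical Exclusion Criteria, item 1, excludes women who are pregnant, lactating, or planning a pregnancy within 7 months. Potential Study Risks adds an instruction not to become pregnant on study, advice to tell staff about a pregnancy, and immediate discontinuation of medication if one occurs.

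**The concern.** Pregnancy status can change between Intake and Day 1, and the protocol does not check it again before giving medication. Required contraception is tied to the time on medication, so the interval has neither a test nor a contraception requirement.

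The Reproductive Risks paragraph says that safety for an unborn baby is unknown. An exposure of this kind would involve no protocol deviation. The rule to stop medication can act only once the pregnancy is known, and Table 2 schedules no pregnancy test at any later visit, while dosing runs to Day 84.

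**Working it through.** The plan states no figure to reproduce. The check sets the schedule and the safeguards side by side, with simple arithmetic for the interval.

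**Length of the interval**

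| Quantity | Source | Result |
|---|---|---|
| Nominal interval | Visit labels, Week -1 to Week 0 | 1 week = 7 days |
| Longest interval without a new Intake | Varenicline or Placebo Treatment section | 60 days |
| Excess over nominal | 60 - 7 | 53 days |
| Ratio to nominal | 60 / 7 | 8.6 |
| First supply dispensed | Pre-Quit Session: 3 weeks × 7 | 21 days |

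Because Table 2 gives no window for Pre-Quit, 60 days is the only stated limit. The ratio describes what the protocol permits; it is not an estimate of risk.

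**Whether each safeguard detects an unrecognised pregnancy within 60 days**

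| Safeguard | Covers the interval? | Detects it? |
|---|---|---|
| Intake urine test | No; it comes before the interval | No |
| Exclusion for planned pregnancy within 7 months | Yes, as to intention | No; an unplanned conception passes |
| Instruction not to become pregnant on study | Yes; Study Duration counts participation from the initial eligibility assessment | No |
| Advice to notify staff | Yes | No; the woman must know |
| Medication stopped on pregnancy | From first dose | No; the pregnancy must be known |
| Required contraception or abstinence | No; starts with medication | No |
| Repeat Intake | Only beyond 60 days | Not within 60 days |

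Reproductive Risks also says that women will be asked to take a pregnancy test before the study starts. The Intake test satisfies that sentence, which does not imply a second test at Week 0.

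**Comparison within the protocol.** Blood pressure is another exclusion that can change with time. It is measured again at Pre-Quit, and a reading above the limit holds back medication until the study physician has been contacted (Medical Exclusion Criteria, item 5; Blood Pressure section). Pregnancy status has no such recheck.

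**Whether delays are foreseeable.** The Intake section allows kidney function tests after the visit, with out-of-range results reviewed by the study physician before enrollment. Several exclusion criteria also call for physician approval. Starts later than one week after Intake can therefore be expected, but the documents do not say how often.

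**The case against.** The strongest reply is that the sponsor saw this interval and set a limit on it. Eligibility holds for 60 days, after which Intake and its pregnancy test are repeated. No passage contradicts another, and the documents contain no standard that 60 days breaches. Women attend Week 0 in person before starting medication, with a concomitant medication review and a side-effect checklist, so a known pregnancy could be reported then. What is left is an unplanned, unrecognised conception, contrary to instruction, in a trial where half the sample receives placebo. The consent form and the Manual of Operations are outside the reviewed text, and either may start the commitment earlier. The one-week trigger for a repeat test is also a matter of judgement.

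Much of this stands. The matter is a design choice and the remaining risk is narrow. The placebo arm means that not every such exposure would be to varenicline. The statement about contraception is limited to the protocol text, and another trigger between 8 and 60 days could be defended. It does not remove the gap: none of these safeguards detects an unrecognised pregnancy inside the window, and the protocol already rechecks blood pressure at the same visit.

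**Conclusion.** The concern holds. On the protocol text, there is no pregnancy test between Intake and first dispensing, an interval of 7 days nominally and at most 60, and the required contraception period has not yet begun. A site following the protocol could give study medication to a woman with an unrecognised pregnancy.

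The importance is small. The documents give no share of women of childbearing potential, no conception rate and no distribution of Intake-to-Day 1 intervals, so no count of affected women can be calculated. The conclusion assumes that neither the consent form nor the Manual of Operations adds an earlier commitment or a Week 0 test. This is an improvement to consider for participant safety; it has no bearing on the trial's results.

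**What to change.** 1. In Key Inclusion Criteria, item 6, and in Reproductive Risks, begin the contraception or abstinence commitment at the Intake Session, and keep its present end point of at least one month after the medication period. This lengthens the commitment by the Intake-to-Day 1 interval, nominally 7 days and at most 60, and adds no procedure.

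2. In the Urine Pregnancy Screen section and Table 2, add a urine test at Week 0, before dispensing, for women of childbearing potential whose Day 1 falls later than the nominal one week after Intake. This costs one kit of a type already in use per delayed woman, at an in-person visit already scheduled.

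No repeat test is proposed for women who start on the nominal schedule. A test so soon after a negative one is judged to add little, and the first change covers their interval. If the consent form or the Manual of Operations already contains either provision, the protocol need only be aligned with it.
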